We propose a community-VHA partnership and peer-led navigation intervention (iNSPiRED, or VeteraN SuPport and REsources for Diabetes) to improve access to Diabetes Self-Management and Education (DSME) and mental healthcare in the VHA or the community for Veterans who have DM and diabetes-related distress. iNSPiRED uses peer coaches/navigators to help Veterans access VHA and community resources, including self-management tools, education, and clinical care for mental health and DM. The format, intensity and location of support will be tailored to each Veteran's motivation and preferences. The VHA's growing use of Veteran peer-support specialists offers an opportunity to employ them to improve DM management and mental health outcomes. Innovative aspects of this proposal include (1) recruitment of Veterans outside the healthcare system, where they are less likely to access or engage in care; (2) use of Veteran peer-support specialists to address DM and mental health through navigation and coaching; and (3) integration of a community-VHA partnership, including reaching out to Veterans not obtaining care in the VHA and providing options for care outside the VHA. Our proposed intervention aligns with the chronic care model by promoting coordinating healthcare delivery

mechanisms, self-management support and community-based resources and is unique among diabetes-related interventions in its explicit inclusion of community resources and partnerships.

Goal The goal of this intervention is to determine if Veteran peer coaches can decrease diabetes-related distress by facilitating use of VHA and non-VHA medical and health-promotion resources and providing support. The 3-month intervention is enhanced by a robust community-engaged partnership developed by [name] and his team between VHA researchers and United Way, Area Agency on Aging, Veteran service organizations, and Veteran-serving community-based organizations.

Aims/Objectives We will evaluate the following outcomes in Veterans with diabetes distress with a randomized trial comparing the iNSPiRED intervention to usual care (print-based referral information and resources):

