PRIMARY OUTCOME a. iNSPiRED Veterans will improve more in diabetes-related distress (17-item Diabetes Distress Scale). **SECONDARY OUTCOMES** b. iNSPiRED Veterans will improve more in diabetes self-management (Diabetes Self-Management Scale). c. iNSPiRED Veterans will improve more in depression symptoms (Patient Health Questionnaire-8 [PHQ-8]) and anxiety symptoms (Generalized Anxiety Disorder scale [GAD-7]). d. iNSPiRED Veterans will be more likely to use health-promotion programs and clinical care and be more likely to newly choose VHA or community health-promotion programs or clinical care.

STAKEHOLDER OUTCOMES We will employ stakeholder engagement activities to increase development and sustainability of VHA-community partnerships, trust, communication and capacity building. A mixed-methods process evaluation will be used to evaluate this aim.

Section E: Protocol Risks/Subjects

E1. Risk Category

Category 1: Research not involving greater than minimum risk.

E2. Subjects

Gender:

Both

Age:

Adult (18-64 yrs), Geriatric (65+ yrs)

Ethnicity:

All Ethnicities

Primary Language:

English

Groups to be recruited will include:

Asymptomatic patients with chronic conditions, healthy; Patients

Which if any of the following vulnerable populations will be recruited as subjects?

Employees or lab personnel, Mentally ill

Vulnerable populations require special protections. How will you obtain informed consent, protect subject confidentiality, and prevent undue coercion?

Although this study involves minimal risk, particular attention will be given to being sure that participants understand that refusing to consent will not affect eligibility to receive any services or benefits from the VA and that confidentiality will be maintained except as allowed by law or as described in the consent document.

Study staff will contact all referrals by phone for initial screening within 48 hours of the initial contact for those referred by community agencies and Veterans Service Organizations and within 10 days for those recruited through opt out letters. For all patients, a telephone script will be used to obtain verbal consent to administer the initial protocol screening. At the initial screen, the study staff will confirm eligibility criteria. Veterans will be screened for distress using the 2-item screening version of the Diabetes Distress Scale (DDS2). Veterans with a mean score of 3 or more will be eligible for the baseline assessment.

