Patients will be eligible to participate in the study if they meet the following criteria:

(1) Veteran (2) Diagnosis of type 2 diabetes mellitus, per self-report (3) Moderate diabetes-related distress (Diabetes Distress Scale [DDS2] mean score of 3 or greater)

Exclusion Criteria:

(1) Lack of reliable access to a telephone (2) Cognitive, sensory, or other impairment that prevents use of a telephone (3) Current participation in another diabetes-related counseling or self-management program

F2. Procedure

Upon providing informed consent, participants will be randomized in blocks of 6 or 8, based on referral source (MEDVAMC and non-MEDVAMC). At the initial screen, the study staff will confirm eligibility. Veterans will be screened for distress using the 2-item screening version of the Diabetes Distress Scale. Veterans with a mean score of 3 or more will be eligible to continue. Veterans who are eligible and wish to participate further will be scheduled for a telephone baseline assessment. They will be mailed a cover letter, informed consent document without signature lines, and copies of baseline assessment instruments. A member of the study team will call and review the consent documents before final enrollment and completion of the baseline assessment.

Usual care. Veterans randomized to the usual care condition will be encouraged to follow-up with their primary care provider and/or specialty providers for management of their health conditions. They will receive a packet of printed information that includes a list of self-management support resources in the VHA and the local community, but no specific recommendations or referrals. The list will be updated periodically with similar resources as needed.

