Peer intervention. The peer intervention will include approximately 5-6 contacts over a 3-month period. Peer coaches are responsible for providing emotional and social support, normalizing the difficulty of living with DM, modeling help-seeking behaviors, and connecting patients with VHA and/or Community-based Organizations (CBOs) to address mental health and DM self-management needs. Peer coaches are not responsible for health education directly, but will encourage patients to use appropriate programs in which mental health and DM self-management services are provided. They will be trained to offer encouragement and basic assistance with problem-solving, activation, achieving self-efficacy, and setting goals. As Veterans with DM or other chronic medical/mental health conditions, peer coaches are ideal guides who help uniquely by sharing their personal stories and modeling. After making an initial introduction by telephone, the peer coach will arrange to meet with the Veteran in person at a mutually suitable place (e.g. a coffee shop, a community agency, a VHA facility) or by telephone, Facetime, GoogleDuo, Zoom or Microsoft Teams with a VA cell phone. Home visits may be allowed for home-bound Veterans pending an evaluation of safety and approval of the PI/his designee. During this meeting, the peer coach will orient the Veteran to his or her role, exchange contact information and preferences for contact, and conduct a needs assessment to identify opportunities to recommend specific resources. Potential mental health resources include counseling and medication referrals, online or in-person support groups, and education materials about distress and mental health conditions. Potential DM resources include online education materials from the ADA, cooking and recipe information, referrals to DM education and dietitians, free and low-cost exercise classes and gyms, and local food banks that have DM-friendly foods. Specific resources for related issues--low-cost primary care clinics, help with sleep problems, and transportation resources for medical appointments--are included. Peer coaches will be trained to probe for additional information as needed and to identify specific unmet needs or experiences of securing help. For instance, a Veteran who reports feeling overwhelmed with a DM regimen may be asked other questions to identify whether he or she has obtained help from a health professional and what solutions have already been tried. As peer coaches come to understand the Veteran's priorities, preferences, and barriers better, they will provide validation and support, offer suggestions for a few applicable community programs, and facilitate goal setting to help the Veteran choose and follow through on recommendations. The peer coach will follow up by phone approximately every 2-3 weeks, based on Veteran needs and preferences. Information and education on DM self-management and psychological well-being may be provided verbally or through the mail and will be tailored to the patient's needs and preferences. Participants will also be provided with a study workbook and goal-setting worksheet. The intervention will end at 3 months, when the Veteran chooses to terminate or after 5 consecutive unsuccessful attempts at contact. To ensure fidelity to the intervention, peers will complete semi-structured session notes after each interaction with a Veteran that will be reviewed by the peer supervisor each week. Session notes will include which resources were provided, whether problem-solving or coaching was used, and progress towards goals.

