
We will develop a brief Memorandum of Understanding between the VA leadership team and each partner outlining: 1. The purpose/goals of the partnership, 2. What they can expect from the VA research team, and 3. What will be asked of them during the course of the project including activities, meetings, and surveys they will be asked to complete as part of the engagement process. Protection Against Risk: Questionnaires. Participants will be informed that if they do not wish to answer specific questions or wish to terminate the session, they will be able to do so.

Adverse Events. In addition to the subject's request, criteria for discontinuing a subject's participation may include, as determined by the Primary Investigator in discussion with the study team, any life-threatening or potentially disabling event, or hospitalization for acute medical or psychological illness. These serious adverse events (SAEs) will be recorded and included in the database. SAEs will be reviewed by the PI and reported to the IRB in accord with VAMC policy. Any subject who develops an SAE during the conduct of study protocols will be referred for immediate medical care at the VAMC or outside medical facility and referred to their physician for ongoing care. Management of Suicidal Ideation (SI) or Behavior. SI with intent or plan is an exclusion for this study. However, given that this is a study of treatment for distress, a plan for addressing suicidal behavior at any time during the study was developed (see section E2).

Section G: Sample Size/Data Analysis

G1. Sample Size

How many subjects (or specimens, or charts) will be used in this study?

Local: 218 Worldwide: 218

Please indicate why you chose the sample size proposed:

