Outcomes: Secondary outcomes. Analyses of the secondary clinical outcomes will be similar to those used for the continuous primary outcomes. We will test assumptions of normality and make transformations as needed. We will then run linear regression models separately for each secondary outcome. The models will include terms for the intervention, time period, time-by-period interaction, the a priori SES and race/ethnicity variables, and the referral source. Significant values for the time-by-treatment interaction will indicate that there were significant differences over time in the secondary outcome. In addition, by dichotomizing the outcomes, we will determine whether the groups differed in having or not having clinically significant changes in PHQ-8 and GAD-7 scores. A 5.0-point decrease in the value of PHQ-8 will be considered a minimally clinically important change⁹⁴ and coded as such; decreases of less than 5.0 points from baseline will be coded as not having achieved clinically significant change. For GAD-7, a score of less than 10 will be considered as having clinical improvement, with scores of 10 or higher representing clinically elevated anxiety symptoms. We will test whether the two groups (clinically significant change vs. no clinical change) differed using a logistic regression model in which the dichotomous outcomes are the dependent variable. The independent variables will be those described above for the linear regression models.

For the secondary outcomes of use of printed/web-based resources, health promotion programs, and clinical care, we will run logistic regression analyses of dichotomized variables (i.e., whether or not the patient used printed/web resources, whether or not he/she used health promotion programs, and whether or not he/she used clinical care during the 6-month follow-up). The models will include terms for the intervention, the a priori SES and race/ethnicity variables, and the referral source. Significant values for the treatment term will indicate that there were significant differences between the iNSPiRED and usual care groups.

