Innovative aspects of this proposal include: (1) recruitment of Veterans outside the healthcare system where they are less likely to access or be engaged in care, (2) use of Veteran peer support specialists to address DM and mental health through navigation and coaching, and (3) integration of a community-VA partnership including outreach to Veterans not obtaining care in the VHA and providing options for care outside of the VHA.

This project will also provide important information about the value of partnering with community-based organizations serving Veterans in order to recruit Veterans who may not go to the VAMC. If shown to be effective, trained therapists in

the VA system can develop relationships with community organizations in order to provide an effective intervention for Veterans who prefer to go to a community-based organization versus the VAMC.

Do anticipated benefits outweigh potential risks? Discuss the risk-to-benefit ratio.

This study involves minimal potential risks to subjects, and measures are in place to minimize these risks. The potential benefits to subjects and society are substantial. Therefore, the potential benefits outweigh the potential risks.

Section J: Consent Procedures

J1. Waiver of Consent

Will any portion of this research require a waiver of consent and authorization?

Yes

Please describe the portion of the research for which a waiver is required. (Example: chart review to determine subject eligibility)

A waiver of consent and authorization is being requested for the recruitment portion of the study:

We will request from the VA Corporate Data Warehouse a list of patients of MEDVAMC who have had at least one visit in the past year with an ICD 10 code for Type 2 DM (E11.x). We will also request a list of patients with an ICD 10 code for Type 2 DM (E11.x) with at least one visit in the past 3 years but no visits in the past year. Variables requested will be name, address, phone numbers, E11x diagnosis code, Scrambled SSN and Real SSN. Real SSN is needed in order to search for updated contact information in CPRS if needed. These subjects will be mailed a letter that describes the purpose of the study, provides contact information for study staff, and invites them to opt-out (a toll-free number will be provided) to the study. Veterans who do not opt out will be called by study staff for screening and consent. This query will be repeated every six months during the recruitment period as needed.

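### The any-versus-none clinical-care outcome is wider than the care the intervention targets, ignores baseline use, and may sit near its ceiling

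*Combined protocol and SAP*

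**What the plan says.** Secondary outcome d in Section D sets the direction: "iNSPiRED Veterans will be more likely to use health-promotion programs and clinical care". G2 (Secondary outcomes) turns the clinical-care part into a yes/no variable, "whether or not he/she used clinical care during the 6-month follow-up", analysed by logistic regression. It gives no type of care, purpose, setting or threshold. On covariates it says: "The models will include terms for the intervention, the a priori SES and race/ethnicity variables, and the referral source". Baseline use is not among them, although F2 lists self-reported use of resources at baseline and month 6.

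Elsewhere the target is narrower. Section D describes the resources that coaches help Veterans reach as "including self-management tools, education, and clinical care for mental health and DM". F2 gives the coaches' task as "connecting patients with VHA and/or Community-based Organizations (CBOs) to address mental health and DM self-management needs", and its list of resources includes counseling, diabetes education, dietitians and low-cost primary care clinics.

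On the control arm, F2 says: "Veterans randomized to the usual care condition will be encouraged to follow-up with their primary care provider and/or specialty providers". On recruitment, J1 and J2 describe "a list of patients of MEDVAMC who have had at least one visit in the past year", a second list of patients seen within three years but not in the last one, and several community routes. No share per route is given.

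**The concern.** A single routine visit makes a participant a user. Such visits may be common in both arms: everyone reports diagnosed diabetes, one recruitment list requires a recent visit, and the control condition itself prompts provider contact. If most controls are already users, little room remains to show a benefit. A null result could then be taken to mean that navigation did not change use of care, when the variable could not have shown a change.

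The content is also a problem at any control rate. A participant who was already seeing a primary care provider and then starts counseling or dietitian care through the coach scores the same as one who only kept a routine appointment. Without a baseline-use term, existing users also blur the comparison. Finally, the rule is silent on acute care. F2 (Adverse Events) treats "hospitalization for acute medical or psychological illness" as a serious adverse event, yet nothing in the definition keeps such a stay from counting as use, and more use counts in favour of the intervention.

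**Working it through.** **The plan's own figures (G1).** Inputs: two-sided 0.05, 80% power, repeated-measures factor (1 + 0.5)/2 = 0.75, attrition 30%. Per arm, n = 2(1.96 + 0.842)²/d² × 0.75/0.70.
- DDS17, d = 0.50: 62.8 → 47.1 → 67.3, against the stated 67 per arm (134).
- PHQ-8 and GAD-7, d = 0.80: 24.5 → 18.4 → 26.3, rounded up to the stated 27 per arm (54). Then 54/0.25 = 216, and 134 × 1.627 = 218.

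These reproduce and are not in dispute. G1 gives no control rate, effect size or power for clinical-care use.

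**Completers.** 218/2 = 109 per arm; 109 × 0.70 = 76.3, taken as 76.

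**Control rate (assumed).** Two illustrative mixtures show how far recruitment moves it:
- 70% from the medical center at 0.97 and 30% community at 0.70: 0.679 + 0.210 = 0.889.
- 30% from the medical center at 0.90 and 70% community at 0.50: 0.270 + 0.350 = 0.62.

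**Power for an odds ratio of 2 (assumed effect).** Treated rate p₂ = 2o/(1 + 2o), where o = p₁/(1 − p₁). Power = Φ[(p₂ − p₁ − 1.96·SE₀)/SE₁], with SE₀ from the pooled proportion and SE₁ from the separate ones.

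Example at p₁ = 0.80: o = 4, p₂ = 8/9 = 0.889, difference 0.0889, SE₀ = 0.0588, SE₁ = 0.0584. (0.0889 − 0.1152)/0.0584 = −0.45, so power is 33%.

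| Control rate | Treated rate | Power, 76 per arm | Power, 109 per arm |
|---|---|---|---|
| 0.50 | 0.667 | 55% | 71% |
| 0.62 | 0.765 | 49% | 65% |
| 0.70 | 0.824 | 43% | 57% |
| 0.80 | 0.889 | 33% | 44% |
| 0.90 | 0.947 | 19% | 26% |
| 0.95 | 0.974 | 12% | 15% |

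**Room to move, 76 per arm.** The treated rate needed for 80% power is 0.72 from a control rate of 0.50, 0.88 from 0.70, 0.95 from 0.80 and 0.999 from 0.90. From 0.95 no treated rate reaches 80%: if essentially everyone treated used care, power would be about 50%. The normal approximation is generous here; Fisher's exact test gives about 18% for that last case.

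**Few non-users.** At 0.90 against 0.947, expected non-users are 76 × 0.10 + 76 × 0.053 = 11.6 across both arms. At 0.95 against 0.974 they are 76 × 0.05 + 76 × 0.026 = 5.8. The logistic model has terms for treatment, income, education, race/ethnicity and referral source.

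**The case against.** The strongest reply is that the ceiling is assumed. F1 makes recruitment of Veterans outside the VHA central to the design, J2 expects to enroll some who are not accessing care, and one of the two clinic lists is of lapsed patients. At a control rate of 0.50 to 0.70 there is no ceiling. This stands. A reader might infer that the sample comes largely from clinic lists and that the outcome will be near 100%, but the documents give neither a recruitment split nor a use rate. Only a conditional statement is supported.

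A reader might also infer that the plan scores a hospital stay as success. It does not say so. Hospitalization appears only in safety text, and the utilization questionnaire is not reproduced, so it may separate inpatient care. What can be said is that the definition does not exclude it.

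G2 also tests new use of VHA care, and then of community care, among baseline non-users of each. That removes existing users and partly offsets the problem. But these tests split by sector, not by type of care: a VHA user who starts counseling within the VHA is left out of the VHA new-use test and may already be a yes on the main variable.

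Two further points stand. Because coaches also link to low-cost primary care clinics, starting primary care is an intended success for someone out of care and must not be discarded. And a narrower outcome might meet a floor: a control rate of 0.111 against 0.200 is also an odds ratio of 2 and also has 33% power.

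**Conclusion.** The point holds in a limited form. The mismatch between the scored variable and the targeted care, the missing baseline-use term and the silence on acute care can be read directly from the documents and do not depend on any rate. The loss of power does. It rests on an assumed control rate, an assumed odds ratio of 2, 30% attrition and an unadjusted comparison. Across assumed control rates of 62% to 95%, power falls from about 49% to 12%. Even with no attrition it is only 26% at 90% and 15% at 95%. A near-ceiling rate is a real risk in this population but not an established fact.

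This is one component of the last-listed secondary outcome, and G1 claims power only for DDS17, PHQ-8 and GAD-7. The conclusion on DDS17 is unaffected.

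**What to change.** Amend G2 for the clinical-care outcome before analysis:

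1. Count outpatient mental health care and diabetes-specific care, such as diabetes education or dietitian care. Score it as any use or, if the questionnaire separates services, as the number of distinct services, and name one of the two as the main analysis. State whether diabetes education counts here or under health-promotion programs, so that it is not scored twice.
2. Add baseline use as a covariate.
3. Keep new primary-care use among baseline non-users as a separate measure.
4. Report emergency and inpatient use separately, and any clinical care descriptively.
5. State the expected control rate, or that it is unknown.

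The cost is analysis-plan wording and recoding of data already planned at baseline and month 6, with no added visits. There are three drawbacks. The change narrows the broad wording of secondary outcome d. It works only if the questionnaire separates service types, which should be checked first. And the control rate of the narrower outcome is also unknown and could be low, so a gain in power is not assured; what is assured is a closer match to the trial's stated aim.
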